Four modules were offered during the next 18 months (phase 2): “Healthy and Fit,” which combined healthy eating patterns and regular exercise to avoid weight gain during the holiday season; “Step Challenge,” which was a team-based module, focusing on increasing physical activity by using a fitness device to track steps; and two consecutive “Nutrition for a Lifetime” modules, which were designed to help employees achieve and maintain a healthy lifestyle by combining healthy nutrition, exercise, stress management and sleep patterns. In addition, participants had the opportunity to log their step counts using a wearable device and this information was gathered between January 2017 and July 2017. Please refer to Appendix 1 for detailed information on the components of the wellness program by module, including requirements and incentives. Employees had opportunities to receive incentive payments through completion of the PHA and the biometric screenings, in addition to participation in the individual modules of the program.

In each treatment worksite, a Registered Dietitian employed by Wellness Workdays coordinated and led the wellness programming. The Registered Dietitians engaged employees in the wellness program modules, educated them about the content of the program, and led employees in various creative activities such as group fitness and cooking demonstrations. Each Registered Dietitian had the flexibility to tailor the day-to-day programming around the themes of the modules. The Registered Dietitians spent approximately 8 hours per week at each worksite.

III. Randomization

The wellness program was implemented in a randomly selected subset of BJ’s Wholesale Clubs. Each club is a standalone worksite, with an average of 118 employees at any given time. At the beginning of the study, there were 201 BJ’s worksites in the U.S. along the East coast, extending from Maine to Florida. We eliminated 41 worksites because they were geographically remote or had employee pools with substantially different insurance coverage from the others, leaving 160 worksites in our sample.

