Health care claims data were provided at the individual employee level by Cigna and were used to calculate spending and utilization variables. These administrative data are available for all worksites (treatment, primary control, and secondary controls), but only for the roughly 37% of employees who were enrolled in a BJ's employer-sponsored Cigna health insurance plan at any given time. Full time workers were more likely to have Cigna coverage than part-time workers. We analyzed medical claims for BJ's employees (but not their dependents, who were not directly exposed to the treatment).

We aggregated medical spending and utilization at the employee level across our 36-month treatment period. To standardize utilization outcome variables across employees who may have been employed and in our sample for different lengths of time, we normalized outcomes for partial-year enrollees to annual values. For each employee, we exclude any claims with service dates prior to either the employee's hire date or the start of Cigna eligibility status as well as any claims with service dates more than 30 days after the employee's termination or end of Cigna enrollment.

We examined the following outcomes at the individual level as well as the worksite level. In worksite-level analyses, results are shown per 2000 work hours for all the continuous outcomes to normalize across sites of different sizes. An exception was the number of distinct medications, which we constructed at the worksite level using a weighted average of individual values based on hours worked at the worksite.

- **Total medical spending:** We defined total medical spending per year as the sum of all payments made for health care – deductibles, copayments, coinsurance, insurance payments, and “amount paid by other carrier” – that appear on an employee's claims.
- **Medical utilization:** We defined three medical utilization variables (i.e. counts of services provided):
 - *Office Visits:* We defined an office visit as a claim line with site of care as “office” or “on-campus outpatient hospitals” and service type as “physician visit.” We counted as one office visit such an occurrence at the level of a unique combination of patient, service date, and provider specialty. In other words, if an office code appears on multiple claim lines on the same date and billed by the same provider specialty, we counted these as a single visit. We do not include office visits that occurred with the site of care as

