In this representative estimating equation, Y_{ijt} denotes an outcome of interest, such as medical spending, for individual i who is employed in worksite j at time t . $TREATMENT_{jt}$ is a binary indicator of whether the individual's worksite was randomized into treatment or control. We assigned each individual to the worksite at which he or she was employed when the treatment began in January 2015. $TIME_WORKED_{ijt}$ is the share of total available work hours in the study period that the individual actually worked; it is expressed in percentage terms. The effect of randomization to a treatment worksite is allowed to vary based on exposure to the treatment (measured via time worked during the treatment period). The treatment effect is captured by $\beta_1 + \beta_3 * Exposure$. The average effect of randomization into the treatment group can be summarized by assessing this at the average level of exposure. While we will produce estimates of the average effect of randomization into treatment, as captured in the layout of Tables 3-6, we will additionally show results for both β_1 and β_3 for each of our results in a set of parallel tables.

X_{ijt} represents a vector of covariates that may help improve precision as well as account for chance differences in characteristics between treatment and control groups, including:

- Age indicators: <20 years (omitted), 20-29, 30-39, 40-49, 50-59, and 60 and greater.
- Sex indicator: male (omitted), female
- Age-sex interactions
- Race: white (omitted), black, Hispanic, and other
- Employment characteristics (measured at baseline for the stably employed subsample):
 - Part-time (omitted), full-time
 - Salaried (omitted), hourly
 - Sales worker (omitted), non-sales worker, and other worker.

ε_{ijt} is the idiosyncratic error term. The models are weighted using the sample weights described above. Standard errors were clustered at the worksite level.

B. Local average treatment effect (LATE)

While our ITT analysis explores the effect of being randomized into a treatment worksite, a related but distinct question is: what is the effect of participating in the wellness program on the outcomes of interest? The answer to this second question will be different if not all employees in treatment worksites elect to participate. Because the choice to participate in the program is endogenous, simply including participation as a right-hand side variable may produce biased

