randomization into treatment or control, with β_1 indicating the average worksite-level effect of being randomized into treatment. The vector of covariates X_{kt} comprises the same set of observable characteristics for individuals, aggregated to the worksite level using weighted averages (generating percentages for binary variables). The worksite-level regressions are weighted by worksite size, as measured by the total hours worked by all employees at a worksite, with standard errors adjusted for heteroscedasticity. For estimates of program effect that are significant in the individual-level analysis, we will produce parallel LATE estimates at the workplace level, analogously using treatment status as an instrument for participation.

Although the employees at each worksite could change over time, the worksites themselves were all stably represented in our data. However, at the 18-month mark, 5 worksites previously in the control group entered the treatment group. In our base specification, we will assess effects for the 20 worksites that were continuously treated throughout the 3-year period (omitting the additional 5 from the analysis altogether). As an alternative specification, we will also evaluate effects at the worksite level when considering the 5 additional worksites in the treatment group.

F. Sensitivity analyses

We conduct several types of sensitivity analyses. First, in the statistical analyses above, our base regression models use linear regression even for binary outcomes. The OLS estimator has been shown to perform better than other non-linear approaches in estimating the average population effect, particularly with large samples.¹⁰ However, OLS also has limitations, such as its sensitivity to outliers. To test the robustness of our main results to changes in functional form, we will fit logit models for binary outcome variables.

Second, we will present LATE results with alternative definitions of participation. As defined above, these include a binary indicator of participation based on completing at least one module, and a high participation indicator defined as completing at least 3 modules.

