Additionally, our phase 1 analysis of the first 18 months used a different baseline specification that did not allow for treatment effects to vary with individuals' exposure (rather, weighting individuals by exposure). It also included a different sample, as 5 additional worksites from the previous secondary control group were added to the treatment group and another 5 to the primary control group at the 18-month mark. Therefore, to facilitate comparisons of results between this phase 2 analysis to those from phase 1, we will present results using the phase 1 statistical model and set of weights on the phase 2 sample, as well as results using the phase 2 model and weights on the phase 1 sample.

Specifically, we conduct the ITT and LATE analyses using the phase 1 specifications that include just a treatment dummy. The ITT specification is:

$$Y_{ijt} = \beta_0 + \beta_1 TREATMENT_{jt} + \beta_2 X_{ijt} + \varepsilon_{ijt} \quad (7)$$

¹⁰ See, for example, Buntin and Zaslavsky, 2004; Manning, Basu, and Mullahy, 2005; Ellis and McGuire 2006; Jiang, Ellis, and Kuo, 2008.

The LATE specification is:

[figure not shown]
$$Y_{ijt} = \gamma_0 + \gamma_1 PARTICIPATION_{ijt} + \gamma_2 \mathbf{X}_{ijt} + \mu_{ijt} \quad (8)$$

With first stage regression:

$$PARTICIPATION_{ijt} = \pi_0 + \pi_1 TREATMENT_{jt} + \pi_2 \mathbf{X}_{ijt} + v_{ijt} \quad (9)$$

[figure not shown]
We conduct this analysis first for our full sample, and then for the subsample of treatment and control sites that match the phase 1 sample.

Figure 1: Locations of Treatment and Primary Control Worksites, Phase 2

Notes: This map shows the 25 treatment and 25 control worksites in Phase 2 of the treatment. Red markers designate treatment worksites; red triangles are the 5 additional treatment worksites that were added in Phase 2. Blue markers designate primary control worksites; blue triangles are the 5 additional primary control worksites that were added in Phase 2.

Figure 2. CONSORT Flow Diagram

Average number of employees per club = 304 (SD =88)
 Employees insured through Cigna during June 2016 (the midpoint of the study period) = 6,686 (37.34%)
 *Surveyed employees as a percent of all employees who worked between 8/1/2017 and 10/30/2017

Notes: This CONSORT diagram shows the flow of the trial and sample sizes through phase 2.

Table 1: Timeline of the Workplace Wellness Program

	Phase 1												Phase 2																							

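### The 5 sites that joined treatment at month 18 are left out of the worksite-level base, yet Table 10 Panel C includes them and the employee-level counts indicate they are coded as treated, with pre-program hours credited as exposure

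*Combined protocol and SAP*

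**What the plan says.** **Worksite level.** Section VI.E reports the late entry ("at the 18-month mark, 5 worksites previously in the control group entered the treatment group"). For the base specification, "we will assess effects for the 20 worksites that were continuously treated throughout the 3-year period", with the other 5 left out. Including them in the treatment group is the alternative specification.

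**Employee level.** Section VI.A does not mention the 5 sites. Its assignment rule is "We assigned each individual to the worksite at which he or she was employed when the treatment began in January 2015". Section IV.A1 and the notes to Table 8 likewise fix status by the initial worksite. Section III lists 25 treatment sites for phase 2, and footnote 5 gives 20 for phase 1. TIME_WORKED "is the share of total available work hours in the study period that the individual actually worked", so it runs over the whole period for everyone.

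**Outcome windows.** For claims, "We aggregated medical spending and utilization at the employee level across our 36-month treatment period", and "we normalized outcomes for partial-year enrollees to annual values". Biometric and personal health assessment (PHA) data come from August to October 2017 (section IV.B).

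**Sensitivity.** Section VI.F plans runs on the sites matching the phase 1 sample. It does not say in words what happens to the 5 sites in those runs.

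**The concern.** A reader will take the employee-level and worksite-level base results as two views of one effect. If one rests on 25 treated sites and the other on 20, a difference between them may only reflect the treated set. A first-stage table built on a different set from the declared base does not describe the instrument used in the worksite-level two-stage least squares (2SLS) analysis.

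The second problem is exposure. Section VI.A includes TREATMENT*TIME_WORKED to show how the effect changes with exposure to the intervention. At the 5 sites, an employee who worked through the first 18 months and then left is credited with treated exposure although no program was available there. This affects spending, utilization, absenteeism, performance and tenure. Section VI.C names tenure among the primary outcomes.

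**Working it through.** **1. Reproduce the plan's counts.**
- Employees (Tables 8 and 10 Panel A): 7,288 + 41,376 = 48,664, as stated.
- Other samples also close: Cigna 1,385 + 7,174 = 8,559; stably employed 2,344 + 13,000 = 15,344.
- Sites (Tables 9 and 10 Panel C): 25 + 135 = 160, as stated.

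**2. Where are the 5 sites at employee level?** Figure 2 gives "Average number of employees per club = 304" (SD 88).
- 48,664/160 = 304.15, which matches. Over 155 sites it would be 314.0.
- 7,288/25 = 291.5 per treated site, close to primary control (7,377/25 = 295.1).
- 7,288/20 = 364.4 would lie (364.4 - 304)/(88/sqrt(20)) = 3.1 standard errors above the mean.

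The sample size equals the number of employees, so each employee has one treatment value and the counts show no time-varying coding. The 5 sites appear as treated for the full period. The 135 control sites alone would not settle this, because that number fits both omitted and treated.

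**3. Declared worksite base against Table 10 Panel C.** The declared base is 20 + 135 = 155 sites. Panel C (All and Cigna columns) has 160 - 135 = 25 treated sites.

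**4. Size for the 10 administrative outcomes** (3 in Table 3, 7 in Table 4), relative to a full 36-month program. Assumptions: a non-zero effect present only while the program runs, equal-sized sites, and control-site turnover at the 5 sites.

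| Basis | Calculation | Smaller by |
|---|---|---|
| Calendar months | 5/25 x 18/36 | 10.0% |
| Module dates, program counted to 31 Dec 2017 | 5/25 x 464/(464 + 413) days | 10.6% |
| Module dates, program ending 30 Jul or 30 Jun 2017 | 5/25 x 464/723 or 464/693 days | 12.8% or 13.4% |
| Modules offered | 5/25 x 8/12 | 13.3% |
| Stably employed, person-time | 5/25 x 58.0% | 11.6% |
| Stably employed, each employee once | 5/25 x 69.1% | 13.8% |

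The day counts start at Module 1 (23 Feb 2015), stop at the end of Module 8 (31 May 2016) and resume at Module 9 (14 Nov 2016).

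*Main-sample turnover.* Section III gives "Each club is a standalone worksite, with an average of 118 employees at any given time". With steady flow, 304 - 118 = 186 employees per site turn over in 36 months. About 93 leave before month 18 and 93 join after it. By symmetry the mean pre-program share stays at 50%, so the 10% by calendar months is unchanged. Check: 118/304 x 1,096 days = 425, against 416.69 in Table 3. Employees gone before their site had a program: 5/25 x 93/304 = 6.1%, about 446 of 7,288.

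*Stably employed.* Appendix 2 gives 75% retention at 1 Dec 2015 and 51% at the end of 2017. I assume 100% to 1 Mar 2015 and straight lines between these points. Check: mean 780 days, against 786.57 in Table 3. About 68.3% remain at month 18, so 5/25 x 31.7% = 6.3%, about 149 of 2,344, left before their site had a program.

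The seven claims outcomes use the Cigna sample. Among controls, 5,779/7,174 = 81% of it is stably employed, so the stably employed rows are the closer guide there.

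**5. Cost of omission.** The standard error (SE) ratio, treating sites as equal units, is sqrt((1/20 + 1/135)/(1/25 + 1/135)) = 1.10. Break-even dilution is 1 - 1/1.10 = 9%, so power is roughly unchanged.

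**The case against.** **A rule can be inferred.** Section III names 25 phase 2 treatment sites, and status follows the initial worksite. Together these imply a 25-site ITT. This stands: it would be too strong to say that the plan leaves status at the 5 sites undetermined. What is missing is an explicit statement, and a reason why the worksite base differs.

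**The estimand is legitimate.** Section VI.A targets the average effect of randomization to a treatment site and never promises the effect of 36 months of program. This also stands. A reader might infer that the employee-level ITT is biased, and the documents do not support that. It answers a different question from the 20-site base.

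**Both treated sets are already planned.** The phase 1-matched runs cover employee level, and VI.E has a 25-site alternative. This is largely right. For administrative data, returning the 5 sites to control would leave all 160 sites, so omission is the natural reading of a subsample. The plan should still say so, because returned sites would put 18 treated months in the control arm. None of these runs corrects the exposure term or Panel C.

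**The numbers are small.** For medical spending, ignoring clustering, SE = 18,559.82 x sqrt(1/1,385 + 1/7,174) = about $545. If the true effect were 10% of the control mean ($480, an assumption), 10% dilution is $48, under 0.1 SE. This stands: the case rests on coherence and interpretation, not on power or on a likely change in significance.

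**The outcome tables are shells.** No outcome table shows a treated count, so the coding is inferred from Tables 8 to 10. That is correct, and it is a reason to state the rule.

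**Conclusion.** The point holds in a limited form. Table 10 Panel C does not match the worksite base declared in VI.E (160 sites against 155). The two base analyses appear to use different treated groups (25 and 20 sites). At the 5 late sites, whole-period TIME_WORKED credits 18 months of pre-program hours as treated exposure.

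Relative to the effect of the 36-month program, the employee-level ITT for the 10 administrative outcomes is roughly 10-14% smaller under the assumptions in the working. Each figure changes one feature at a time, so combining them could go slightly above the range. The distortion of the TREATMENT*TIME_WORKED slope has not been quantified.

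Two wider readings are not supported. Biometric and PHA outcomes were measured once all 25 sites were in the program, so they are affected only because the 5 sites were offered 4 of the 12 modules. The local average treatment effect (LATE) per module need not be diluted, because modules completed fall along with modules offered. Nor do the documents show that the employee-level base must change to 20 sites: that is a trade-off, with an SE about 10% higher.

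**What to change.** 1. **Table 10 Panel C.** Rerun the All and Cigna columns on the 155-site base, or label the present figures as the 25-site alternative and add the 155-site first stage.
2. **Employee-level administrative outcomes.** Declare which treated group is the base, and report both sets at both levels. Either:
   - apply the 20-site rule of VI.E, with 25 sites as the alternative; or
   - keep 25 sites, name the estimand as an ITT with staggered start, and do not credit hours worked at the 5 sites before month 18 as program exposure in TREATMENT*TIME_WORKED (equation 1, and the matching term in equation 4).
3. **Phase 1-matched run in VI.F.** State that for the 36-month data the 5 sites are omitted and not returned to control.

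The biometric and PHA analyses may keep 25 sites if the plan says so, and the balance tables may still show all 25.

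The cost is SAP wording and a rerun. The 20-site option also needs balance weights rebuilt on that set, raises the SE by about 10%, and would leave administrative and survey outcomes on different sets if the latter stay at 25. The 25-site option needs the exposure variable rebuilt for the 5 sites. Section I says that three-year outcomes have not been compared by arm, so either choice can still be made without sight of that comparison.

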Administrative data consist of employment records and medical and pharmaceutical claims data. Employment records are available for all employees across treatment and control worksites (both primary and secondary controls). Medical and pharmaceutical claims data are available through Cigna for BJ's employees who are insured through a Cigna plan. In cross-section, approximately 37 percent of all BJ's employees were insured through Cigna during June 2016 (the midpoint of phase 2). Of note, BJ's as an organization is self-insured (i.e. it bears risk of health care spending of its enrolled members), with Cigna as the administrator of its health plans. We used all administrative data available for the entire study period.

A1. Employment records

BJ's provided us with data from their earnings database, which includes data elements that we use both to define our sample (based on hire and termination dates) and to measure key outcomes, such as absenteeism and performance reviews. Information included:

- **Dates and location of employment actions:** Dates and sites of hire, rehire, termination, transfer, and performance review. These data capture employment history across clubs. A small proportion of employees (4.5%) appeared in more than 1 worksite during the study period. We defined these workers' treatment or control assignment using the randomized assignment of their initial worksite, as the decision to leave (or stay) at a worksite could be endogenous. Most employees have one performance review per calendar year.
- **Demographic characteristics:** Characteristics of the working population include age, sex, and race. These are discussed in greater in the section on Analysis below. Worksite level analyses, as described below, were augmented using 2015 estimates of county-level demographic characteristics from the U.S. Census Bureau matched to the locations of each worksite.
- **Employment characteristics:** Characteristics of an individual's job include type of hired arrangement (full time salaried, full time hourly, and part time hourly) and type of job. The types of jobs were grouped into three categories: sales, non-sales (including laborers and helpers, operatives, and service workers), and other (including administrative support, craft workers, and first/mid-level office professionals).

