We designed our analyses based on two study samples. Our main study sample comprised all employees who worked for any duration of time at BJ’s Wholesale Club during the study period. In other words, we included any worker who worked at BJ’s for any length of time during the study period. This is the most inclusive sample.

A potential drawback of these sample inclusion criteria is the possibility of endogenous entry or exit based on the treatment itself. For example, a worker’s decision to join or leave employment at BJ’s Wholesale Club could be a function of the availability of, or exposure to, the wellness program. Therefore, we also defined a relatively stable subsample of employees who were continuously employed at BJ’s in the months before the treatment. This “stably employed” subsample comprised all employees working at BJ’s during, at minimum, the 13 consecutive weeks immediately prior to the onset of the treatment—and thus cannot have entered because of the treatment. Exit from this sample might still be endogenous in theory, however. We will therefore gauge the potential bias introduced by any observed differences in exit between treatment and control sites using a bounding exercise. Additional details on the construction of this subsample are provided below and in the appendix.

B. Balance between treatment and control

We tested balance between treatment and control groups on observable baseline characteristics. We examined balance on demographic variables (age, sex, and race) for all of the analytical samples. We also examined balance on job and employment characteristics in the pre-intervention period for the stably employed subsample, as they by construction were in jobs with characteristics defined prior to the intervention and thus exogenous to the treatment status.

As **Table 8** demonstrates at the employee level, our randomly assigned worksites were balanced on many employee characteristics, but not all. Notably, while treatment and control site workers

⁸ This indicator was our primary definition of participation in our prior phase 1 analysis. Given that we expanded the sample size for phase 2 (with a different total number of modules available), we believe the continuous measure is preferable here.

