The key identifying assumption is that the only mechanism through which being employed in a treatment worksite affects outcomes is through the availability of the wellness program. There are two threats to this assumption. First, to the extent that covariates were not balanced at baseline and those covariates affect the outcomes of interest, that imbalance could bias our estimates. We control for observed covariates and apply weights to balance covariates between treatment and control. Despite these adjustments, unobserved covariates might still be imbalanced.

Second, to the extent that the wellness program affected hiring or tenure of employees, their presence in the data set may be endogenously determined. We address the issue of endogenous entry by pre-specifying a subsample of those who were already employed at the time the intervention began. We defined this more restrictive “stable employment” subsample as comprising employees who had worked continuously for 13 weeks prior to the wellness program. This comes at a cost of reducing the overall sample size. Our goal in choosing the definition for this subsample was to balance the costs and benefits, as detailed in Appendix 2.

In this stably employed subsample, however, exit from the firm's workforce is still potentially endogenous. We deal with this concern in two ways. First, we will test balance on exit between treatment worksites vs. from control worksites overall and for subgroups. Indeed, tenure and time worked are among our primary outcomes. To the extent that we observe any unbalanced exit, we will perform a bounding exercise (assuming that those who exited have outcomes working against any observed effects of the intervention).

D. Subgroup analyses

We pre-specified three subgroup analyses. We selected these subgroups based on differences in key outcomes within the control group for those with different baseline characteristics, such as differences in medical spending by age or in reported exercise by sex (**Table 11**).

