Full-time salary	4.7	7.0	21.3	11.6	12.1	21.7	11.5	11.4	21.8
Full-time hourly	37.4	44.3	66.6	38.6	52.4	66.8	49.0	53.6	66.4
Part-time hourly	57.9	48.7	12.1	49.8	35.5	11.4	39.5	35.0	11.8
Worker Type (%)									
Sales worker	43.2	45.3	23.2	38.4	39.0	22.3	36.2	39.3	23.3
Non-sales worker	45.9	41.8	52.4	46.4	42.8	52.8	47.4	43.7	51.6
Other worker	10.9	13.0	24.4	15.3	18.2	25.0	16.5	16.9	25.0

Notes: Table lists demographic characteristics for the sample covered by Cigna weighted by months of Cigna coverage. About a third of the total sample has Cigna coverage. Age is defined as age at the mid-point of the treatment period (June 2016). This is different from the balance table where age is defined as of December, 2014 (pre-treatment). Thus the means of age in this table are larger than those in the balance table across all samples.

Table 3: Impact on Employment

	Employee-level			Stably Employed Subsample			Worksite-level		
	Mean Value in Control Group (1)	Reduced Form (Linear) (2)	2SLS (Linear) (3)	Mean Value in Control Group (1)	Reduced Form (Linear) (2)	2SLS (Linear) (3)	Mean Value in Control Group (1)	Reduced Form (Linear) (2)	2SLS (Linear) (3)
Absenteeism (%)	2.23 (2.30) 41,376			3.39 (1.97) 13,000			2.90 (0.35) 135		
Performance Review (% ≤ 3)	46.59 (49.88) 27,150			63.64 (48.11) 12,916			65.94 (12.41) 135		
Tenure [§]	416.69 (399.87) 41,376			786.57 (376.96) 13,000			76.08 (4.35) 135		

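### In the main sample 34% of controls have no performance review, so the all-employee performance estimate is conditional on a post-randomisation event that the plan does not address and could be biased in either direction.

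*Combined protocol and SAP*

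**What the plan says.** Section V.A sets no minimum tenure for the main sample: "Our main study sample comprised all employees who worked for any duration of time". On how often employees are reviewed, Section IV.A1 says "Most employees have one performance review per calendar year". It averages each employee's scores, weighted by how long each score held, and dichotomises the result. It gives no rule for an employee with no score.

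Table 3 (control group: mean, SD, number) shows:
- main sample: performance review "46.59 (49.88) 27,150", tenure in days "416.69 (399.87) 41,376";
- stably employed subsample: performance review "63.64 (48.11) 12,916", tenure "786.57 (376.96) 13,000";
- worksite level: performance review "65.94 (12.41) 135".

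Sections V.A and VI.C recognise that entry and exit may be endogenous. The response is the stably employed subsample, a test of balance on exit, and a bounding exercise if exit is unbalanced. Section VI.C introduces the test and the bounding with this sentence: "In this stably employed subsample, however, exit from the firm's workforce is still potentially endogenous". The same section counts tenure and time worked among the primary outcomes.

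**The concern.** Absenteeism and tenure are observed for every main-sample control, but performance review is missing for a third of them. With roughly annual reviews and a sample that admits any length of employment, having a review probably depends on how long a person was employed. The trial treats that as something the program may change. A comparison of reviewed employees by arm is then not a pure effect of randomisation: if the program alters who gets reviewed, the two reviewed groups differ in make-up even if nobody's performance changed.

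Adjustment for TIME_WORKED in equation (1) does not repair this, because that variable is itself post-randomisation. The bounding in Section VI.C is attached to the subsample in which almost everyone has a review. It also assumes that exiters' outcomes run against the observed effect, which gives no direction when the observed effect is near zero. At stake is what can be concluded from the all-employee performance row of Table 3.

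**Working it through.** **Reproducing the stated figures.** For a binary outcome SD = √(p(1−p)). With p = 0.4659 this is 49.88, as stated. With p = 0.6364 it is 48.10 (stated 48.11, rounding). The row is therefore a proportion among reviewed employees.

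**Missing reviews (Table 3 counts, controls).**
- Main sample: 41,376 − 27,150 = 14,226; 14,226/41,376 = 34.4%.
- Stably employed: 13,000 − 12,916 = 84; 84/13,000 = 0.65%, so 99.4% are reviewed.
- Outside the subsample: 41,376 − 13,000 = 28,376 employees, of whom 27,150 − 12,916 = 14,234 are reviewed (50.2%) and 14,142 (49.8%) are not.

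**Tenure outside the subsample.** (416.69 × 41,376 − 786.57 × 13,000)/28,376 ≈ 247 days, against 787 inside.

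**Good ratings among reviewed controls outside the subsample.** (0.4659 × 27,150 − 0.6364 × 12,916)/14,234 ≈ 31%, against 63.64% inside. This combines weighted means with unweighted counts, and the balance weights are not published. If the subsample's weighted share of reviewed controls is 40% to 55% (12,916/27,150 = 47.6% unweighted), the result runs from 35% to 26%.

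**Shift from selection alone.** Let s = 65.6% be the reviewed share in controls, d the rise in that share under treatment, and q the percentage good among the extra reviewed employees. With no true effect, the apparent effect is (s × 46.59 + d × q)/(s + d) − 46.59. The documents do not give the treated arm's reviewed share, so d and q are assumptions.

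| d (points) | q = 20% | q = 31% | q = 63.64% |
|---|---|---|---|
| 2 | −0.8 | −0.5 | +0.5 |
| 5 | −1.9 | −1.1 | +1.2 |
| 10 | −3.5 | −2.1 | +2.3 |

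**Two-sided trimming bounds around an observed zero.** The treated share to trim is p = d/(s + d).
- d = 3: p = 0.03/0.686 = 0.0437. Lower: (0.4659 − p)/(1 − p) − 0.4659 = −2.4 points. Upper: 0.4659/(1 − p) − 0.4659 = +2.1 points.
- d = 5: p = 0.05/0.706 = 0.0708; −4.1 to +3.6 points.

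The bounds assume monotonicity: treatment never removes a review that would have happened under control.

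**Scale.** From the worksite SD in Table 3, the unadjusted standard error of a worksite-level difference is about 12.41 × √(1/25 + 1/135) = 2.7 points.

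**The case against.** A reader might infer that a program which improves retention would necessarily read as worse performance. The documents do not support that. The sign depends on who is retained: if the extra reviewed employees were rated like the stable group, the shift would be upward (last column of the table), and the trimming bounds are nearly symmetric around zero.

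A reader might also take the whole 34% as people who left before a review. The plan never says why reviews are missing. The window runs to December 2017 and Table 3 counts tenure only within it, so late hires may be unreviewed, and have short tenure, without having left. Nor are those outside the stable subsample all new hires; they are those who did not meet the 13-week criterion.

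The plan is also not silent on the subject. It names endogenous entry and exit as a drawback of the main sample. It shows the stably employed estimate in the same row. It will report the effect on tenure in the main sample, and Section VI.C promises the exit test overall and by subgroup. Only the bounding is confined to the subsample. The worksite-level column weights by hours, so short-tenure employees count for little; its control mean of 65.94% is near the stable group's figure and far from 46.59%.

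Finally, the sizes rest on assumed rises and on a raw difference in proportions, not on equation (1), and the likely shift is below the worksite-level standard error.

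All of this stands and limits the point. It does not remove it. A tenure comparison does not show whether the reviewed share differs by arm, no rule covers the unreviewed in the main sample, and the plan does not say which column carries the performance conclusion.

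**Conclusion.** The point holds in limited form. The main-sample performance outcome is missing for 34.4% of controls, probably in large part because of tenure, and the employee-level estimate is conditional on that post-randomisation event. It could be biased either way if the program changes who is reviewed. With better retention, downward is the likelier direction, because reviewed controls outside the stable subsample are about 31% good (roughly 26% to 35%) against 63.64% inside. If the extra reviewed employees resemble that 31% group, the shift is about 0.5 to 2 points for an assumed rise of 2 to 10 points in the reviewed share. This is modest beside sampling error, but adding employees would not reduce it.

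The problem concerns one employment outcome, chiefly in the main-sample columns. In the stably employed subsample it is negligible.

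**What to change.** In Table 3:
- (a) add ever having had a performance review as an outcome, by arm, on all employees;
- (b) state that the performance conclusion rests on the stably employed estimate (99.4% of controls reviewed), and label the all-employee row as conditional on review;
- (c) if (a) differs by arm, show two-sided trimming bounds for the all-employee reduced-form difference, computed with the balance weights and worksite clustering, with the monotonicity assumption stated.

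No new data are needed. The plan says that three-year outcomes had not yet been compared between arms, so the rule should be fixed before that comparison. The cost is a smaller sample for the performance conclusion (12,916 against 27,150 controls), a conclusion limited to people already employed before the program began, and some extra analysis, since the bounds need explicit rules for weights and clustering.
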